12.4.2 Adverse Events

Safety will be assessed based on medical history, vital sign measurements, physical examination findings, ECG results, MUGA or ECHO, liver function test results, ECOG performance status, and laboratory assessments. Adverse events and SAEs will be reported until 28 days after the last dose of investigational product(s) and will be followed until resolution or until condition stabilizes. Should an Investigator be made aware of any SAE occurring any time after the reporting period, it must be promptly reported.

All safety endpoints will be summarized by treatment group and visit when appropriate. Adverse events and SAEs will be coded using the Medical Dictionary for Regulatory Activities (MedDRA) coding system v.15 or later and will be tabulated by system organ class (SOC) and preferred term. All AEs will be graded according to the NCI CTCAE v.4.0. Differences in the incidence of the most common AEs and SAEs between the two treatment groups will be investigated using a CMH chi-square test, stratified on hormone receptor status, prior number of HER2-directed regimens in the metastatic setting, geographic region, and visceral or non-visceral only disease.

A patient who experiences the same AE more than once within a SOC or preferred term category will be counted only once, using the worst toxicity grade for that event.

Serious adverse events and deaths will be provided in a listing. Treatment-emergent adverse events (TEAEs) leading to treatment discontinuation, dose modification, dose hold, and/or delay of investigational product will be tabulated by SOC, PT, and treatment group.

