Guidelines for adjusting doses of **neratinib** in the event of pulmonary toxicity are shown in Table A2. 3. Interstitial lung disease, which can sometimes be fatal, has been reported with other oral tyrosine kinase inhibitors that target HER1 \pm HER2, including **lapatinib**, gefitinib and erlotinib. Rare cases of pneumonitis (0.6%) and lung infiltration (0.4%) have been reported in patients treated with **neratinib** monotherapy, and were considered drug-related. Patients receiving **neratinib** should be monitored for acute onset or worsening of pulmonary symptoms such as dyspnea, cough and fever and treated appropriately.

Table A2. 3 Pulmonary Toxicities Requiring Dose Adjustment of Neratinib

NCI CTCAE v.4.0	Actions
Grade 2 Pneumonitis/Interstitial Lung Disease: Symptomatic; medical intervention indicated; limiting instrumental activities of daily living.	
 Hold neratinib until recovery to Grade ≤ 1 or baseline. Reduce neratinib to 160 mg or discontinue neratinib per Investigator's best medical judgment.
Grade ≥ 3 Pneumonitis/Interstitial Lung Disease: Severe symptoms; limiting self-care activities of daily living; oxygen indicated.	
 Discontinue neratinib permanently.

Abbreviations: NCI CTCAE v.4.0: National Cancer Institute Common Terminology Criteria for Adverse Events Version 4.0.

Liver Toxicity

Guidelines for dose adjustment of **neratinib** and **capecitabine** in the event of liver toxicity are shown in Table A2. 4.

Abnormal values in ALT concurrent with abnormal elevations in total bilirubin that meet the criteria outlined below in the absence of other causes of liver injury are considered potential cases of drug-induced liver injury (potential Hy's Law cases) and should always be considered important medical events.

Patients who experience Grade ≥ 3 diarrhea requiring IV fluid treatment or any signs or symptoms of hepatotoxicity such as worsening of fatigue, nausea, vomiting, right upper quadrant pain or tenderness, fever, rash or eosinophilia should be evaluated for changes in liver function tests. Fractionated bilirubin and PT must also be collected during hepatotoxicity evaluation.

Table A2. 4 Liver Function Test Abnormalities Requiring Dose Adjustment of Neratinib and Capecitabine

NCI CTCAE v.4.0	Actions

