ALT >3 x ULN and Total bilirubin >2 x ULN and Alkaline phosphatase <2 x ULN (potential Hy's law indicators of drug-induced liver damage)	
 • Hold neratinib and capecitabine. The patient should return to the investigational site and be evaluated as soon as possible, preferably within 48 hours from awareness of the abnormal results. This evaluation should include laboratory tests, detailed history and physical assessment and for oncology studies, the possibility of hepatic neoplasm (primary or secondary) should be considered. In addition to repeating AST and ALT, laboratory tests should include albumin, total bilirubin, direct bilirubin, PT and alkaline phosphatase. A detailed history, including relevant information, such as review of ethanol, concomitant medications, recreational drug and supplement consumption, family history, sexual history, travel history, history of contact with a jaundiced patient, surgery, blood transfusion, history of liver or allergic disease, and work exposure, should be collected. Further testing for acute hepatitis A, B, or C infection and liver imaging (e.g., biliary tract) may be warranted. All cases confirmed on repeat testing as meeting the criteria mentioned above (i.e., ALT >3 x ULN associated with bilirubin >2 x ULN and alkaline phosphatase <2 x ULN), with no other cause for liver function test abnormalities identified at the time should be considered potential Hy's Law cases, irrespective of availability of all the results of the investigations performed to determine etiology of the abnormal liver function tests. Such potential Hy's Law cases should be reported as SAEs. • Contact the Sponsor immediately to discuss next steps, including evaluation of alternative causes, and management of investigational product. • These events must be reported as SAEs.

Abbreviations: ALT: alanine aminotransferase; AST: aspartate aminotransferase; BID: twice daily; PT: prothrombin time; SAE: serious adverse event; ULN: upper limit of normal.

NOTE: During evaluation of hepatotoxicity, bilirubin must be fractionated, PT must be measured, and liver imaging should be considered.

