Abbreviations: ADL: activities of daily living; BID, twice daily; IV: intravenous; NCI CTCAE v.4.0: National Cancer Institute Common Terminology Criteria for Adverse Events Version 4.0.

Pulmonary Toxicity

Guidelines for adjusting doses of lapatinib in the event of pulmonary toxicity are shown in [Table A2. 10](#).

Table A2. 10 Pulmonary Toxicities Requiring Dose Adjustment of Lapatinib

NCI CTCAE v.4.0	Action
Grade \geq3 Pneumonitis/Interstitial Lung Disease: Severe symptoms; limiting self-care ADL; oxygen indicated.	Discontinue lapatinib treatment permanently.

Abbreviations: ADL: activities of daily living; NCI CTCAE v.4.0: National Cancer Institute Common Terminology Criteria for Adverse Events Version 4.0.

Hepatic Toxicity

Guidelines for adjusting doses of **lapatinib** and **capecitabine** in the event of hepatic toxicities are shown in Table A2. 11.

Table A2. 11 Liver Function Test Abnormality Requiring Dose Adjustment of Lapatinib and Capecitabine

NCI CTCAE v.4.0		Action
ALT or AST Grade 3: >5-20 x ULN; >5 x ULN for >2 weeks. OR ALT or AST Grade 4: >20 x ULN AND Total bilirubin > 2 x ULN		
 Discontinue lapatinib permanently.
Grade 3 hyperbilirubinemia (>3-10 x ULN)		
 Discontinue lapatinib permanently. Hold capecitabine until hyperbilirubinemia resolves or decreases to Grade 1 (ULN-1.5 x ULN) or Grade 2 (>1.5 x ULN). Reduce next capecitabine dose to 1500 mg/m² (750 mg/m² BID).
Grade 4 hyperbilirubinemia (>10 x ULN)		
 Discontinue lapatinib and capecitabine permanently. OR If the Investigator deems it to be in the patient's best interest to continue, hold capecitabine until event has resolved to Grade ≤ 1 (ULN-1.5 x ULN). If the Investigator decides to resume capecitabine, reduce capecitabine dose to 1000 mg/m² (500 mg/m² BID).
LAPATINIB Dose Adjustment in Subjects with Severe Hepatic Impairment (Child-Pugh Class C)		
Test	Result	
 HER2+ MBC: Reduce lapatinib dose to 750 mg. HR+, HER2+ breast cancer: Reduce lapatinib dose to 1000 mg.
Total bilirubin	≥2 mg/dL; ≥34 μmol/L	
Serum albumin	≤35 g/L	
PT INR	≥1.7	
Ascites	Mild to Severe	
Hepatic encephalopathy	Grade 1-2 (or suppressed with medication) Grade 3-4	

Abbreviations: ALT: alanine aminotransferase; AST: aspartate aminotransferase; NCI CTCAE v.4.0: National Cancer Institute Common Terminology Criteria for Adverse Events Version 4.0; ULN: upper limit of normal.

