9.5.5. Liver Function Test Results

A listing will be generated for patients potentially meeting Hy's Law criteria (total bilirubin \geq (2xULN) and AST or ALT $>$ (3xULN) at any time during the study). Plots or tables of on-therapy peak total bilirubin vs. peak AST (or ALT) will also be generated to help identify potential Hy's Law cases.

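### SAE reporting of potential Hy's Law cases is mandated only under the neratinib liver table, so hepatic SAE counts by arm may not be comparable

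*Protocol*

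**What the plan says.** Appendix 2 of the protocol is split by arm. The neratinib part has a table titled "Liver Function Test Abnormalities Requiring Dose Adjustment of Neratinib and Capecitabine" (A2.4). Its text and table do three things for the pattern ALT >3 x ULN, total bilirubin >2 x ULN and alkaline phosphatase <2 x ULN:

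- The text above the table classes such cases, when no other cause of liver injury is present, as important medical events in every instance.
- The table row requires a work-up and immediate contact with the sponsor.
- The row gives the SAE instruction twice: "Such potential Hy's Law cases should be reported as SAEs", and then, as a separate bullet, "These events must be reported as SAEs".

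The lapatinib part has the table "Liver Function Test Abnormality Requiring Dose Adjustment of Lapatinib and Capecitabine" (A2.11). It contains dose actions only. The one row that brings in bilirubin above 2 x ULN says "Discontinue lapatinib permanently" and nothing about seriousness or reporting.

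On analysis, Protocol 12.4.2 says: "Differences in the incidence of the most common AEs and SAEs between the two treatment groups will be investigated using a CMH chi-square test". SAP 9.3 tabulates SAEs by system organ class, preferred term and arm, and names no test for them. SAP 9.5.5 adds a laboratory-based screen in the safety population: "A listing will be generated for patients potentially meeting" Hy's Law criteria, there defined as total bilirubin at or above 2 x ULN with AST or ALT above 3 x ULN.

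**The concern.** Whether a laboratory finding counts as an SAE should not depend on the assigned arm. Both arms receive capecitabine, and both liver tables contain rules for stopping treatment, so the documents give no reason for a one-arm reporting rule. Two things follow if the text is applied as written.

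- **Comparability.** SAE tables by arm would include hepatic events that enter by rule in one arm and by judgment in the other. The trial is open-label, so the investigator knows which table applies. Any distortion runs against neratinib.
- **Safety reporting.** A control patient with the same pattern has no mandated expedited route to the sponsor. This point does not depend on how common the pattern is.

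**Working it through.** The plan states no figure on this point, so there is none to reproduce. The check is mainly a comparison of texts.

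**Step 1. The rule in each place**

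| Place | Applies to | What it says about this pattern |
|---|---|---|
| Table A2.4 and the text above it | Neratinib arm | Definition, work-up, sponsor contact, SAE instruction given twice |
| Table A2.11 | Lapatinib arm | No such row, no alkaline phosphatase criterion, no SAE instruction |
| Section 13.1.2 | Both arms | A result that changes dosing is an AE; no liver criterion |
| Section 13.1.3 | Both arms | Other important medical events are left to judgment and are usually serious; no liver criterion |
| Section 13.3 | Both arms | SAEs within 24 hours; no liver criterion |
| SAP 9.5.5 | Both arms | Laboratory listing only; creates no SAE |

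**Step 2. One patient under each arm's text.** Take ALT 4 x ULN, bilirubin 2.5 x ULN and normal alkaline phosphatase, confirmed on repeat with no other cause found.

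- On neratinib, all three A2.4 criteria are met (4 > 3, 2.5 > 2, normal < 2). The case is an SAE and falls under the 24-hour rule.
- On lapatinib, the ALT/AST criteria of A2.11 start above 5 x ULN and its hyperbilirubinemia rows start above 3 x ULN, so the values reach neither. If dosing changes, Section 13.1.2 makes the result an AE. It becomes an SAE only if a Section 13.1.3 outcome occurs or the investigator judges it an important medical event.

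**Step 3. Possible size.** Inputs:

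- Patients per arm: 600 / 2 = 300 (Protocol 12.7).
- True rate r of the pattern, equal in both arms: not in the documents; assumed 0.5% to 2%.
- Share q of control cases that still become SAEs: not in the documents; shown at 0.5 and 0.
- Every neratinib case is counted as an SAE, which is the broadest reading of A2.4.

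Artificial excess in the neratinib arm = 300 x r x (1 - q).

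| r | Neratinib SAEs (300 x r) | Excess, q = 0.5 | Excess, q = 0 |
|---|---|---|---|
| 0.5% | 1.5 | 0.75 | 1.5 |
| 1% | 3 | 1.5 | 3 |
| 2% | 6 | 3 | 6 |

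The last column is a ceiling. It requires that no control patient with the pattern is hospitalized, dies or is judged to have a serious event.

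**Step 4. What a test would do with this (illustration only; the plan names no such test).** For a stand-alone comparison of these SAEs, with i and j events in 300 patients per arm and p = (i + j)/600, take z = (|i - j|/300) / sqrt(p(1 - p) x 2/300) and reject if z > 1.96. Summing over the binomial probabilities, with equal true rates, gives these rejection rates:

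| r | Equal reporting | q = 0.5 | q = 0 |
|---|---|---|---|
| 0.5% | 0.030 | 0.033 | 0.065 |
| 1% | 0.046 | 0.094 | 0.353 |
| 2% | 0.049 | 0.158 | 0.851 |

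With the same rule in both arms, the rate stays at or below the nominal 0.05 in this range. With unequal rules, the effect is negligible when the pattern is very rare and grows with r and with under-reporting in the control arm.

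**The case against.** The strongest reply concerns consequence, since the text itself is not in dispute.

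- **The planned test probably does not reach these events.** A reader might infer that the protocol tests hepatic SAEs between arms and that the comparison is biased by design. The documents do not support that. Section 12.4.2 limits the CMH test to the most common events, which a handful of cases would hardly be. The SAP only tabulates SAEs, and no safety comparison is in the alpha hierarchy of SAP 8.3. This stands: the exposure is in descriptive counts by arm.
- **Control cases are not lost.** A reader might infer that serious liver injury on lapatinib goes unreported. Section 13.1.3 still captures death, life-threatening events and hospitalization, and important medical events by judgment. A result that changes dosing is at least an AE. This also stands. What remains is a case judged non-serious, which has no 24-hour duty.
- **The neratinib rule may be narrower than it looks.** The text above A2.4 and one sentence in the row limit it to confirmed cases with no other cause, while the closing bullet carries no condition. Both readings are open, and the narrower one shrinks the excess.
- **An arm-neutral screen exists.** The SAP 9.5.5 listing and the plots or tables of peak bilirubin against AST or ALT apply one criterion to both arms. This largely answers the comparability problem if it is used for the comparison, but it does not correct SAE counts or speed up reporting.
- **The direction is against the sponsor's own drug.** That is true. It makes the asymmetry less worrying for approval but does not make the counts comparable.

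**Conclusion.** The asymmetry is real. The SAE mandate stands only under the neratinib heading, and no both-arm section supplies an equivalent. By-arm hepatic SAE counts are at risk of bias against neratinib, and control patients lack a mandated expedited route for the same finding.

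The size is unknown and probably a few cases at most. The range of 1.5 to 6 SAEs is a gross ceiling under an assumed rate of 0.5% to 2% and no control reporting. With half of the control cases reported, it falls to 0.75 to 3. The rejection rates in Step 4 rest on the same assumptions and on a test that is not planned, so they show direction and should not be read as error rates of this trial. PFS and OS are unaffected.

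A reader might also conclude that SAP 9.5.5 should be brought into line with A2.4. That would be a step back: the SAP screen accepts AST or ALT and sets no alkaline phosphatase condition, so A2.4's criteria would drop cases from a broader screen already applied to both arms. One caution about the listing remains. The instruction to check liver tests after Grade 3 or worse diarrhea needing IV fluids, or after symptoms of hepatotoxicity, also stands only under the neratinib heading, so unscheduled testing may differ by arm.

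**What to change.** - Move the potential Hy's Law definition and its SAE-reporting requirement from Table A2.4 to Sections 13.1.3 and 13.3, so that they apply to both arms.
- State there whether the rule covers every case meeting the laboratory criteria or only cases confirmed on repeat with no other cause found.
- Keep the SAP 9.5.5 listing with its broader criteria and name it as the basis for the between-arm hepatic comparison. A repeat on scheduled samples only would show whether unequal unscheduled testing matters.
- Reconcile Protocol 12.4.2 with SAP 9.3 on whether SAEs are tested or only tabulated.
- If data collection is already complete, make the laboratory-based comparison and disclose the unequal reporting rule beside the SAE tables in the study report.

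The dose actions in the two tables are a separate clinical matter and need no change for this. The cost is protocol wording, a site memo and a few more expedited reports from the control arm.

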Starting Dose	2000 mg/m ² , 1000 mg/m ² BID
-1	1500 mg/m ² , 750 mg/m ² BID
-2	1000 mg/m ² , 500 mg/m ² BID

Abbreviation: BID: twice daily

If doses of investigational product are held, study procedures for that cycle will proceed on schedule as planned, without any delay. This also applies to tumor assessments, which should continue to be done every 6 weeks, starting from the first dose of investigational product until the first planned tumor assessment at 6 weeks (± 3 days), and then after every subsequent 6 weeks (± 3 days) of treatment regardless of any changes in dose or occurrence of AEs. Missed dose(s) of investigational product (i.e., any dose that is not administered within the protocol-defined administration window) will not be made up. The dose adjustment guidelines represent the minimum set of measures that Investigators must follow. However, additional measures may be taken, as necessary, for certain patients per the Investigator's medical judgment. All dose modifications/adjustments should be documented in the patient's source file.

Once an investigational product dose has been reduced for a patient, all subsequent cycles must be administered at that dose, unless further dose reduction is required. Dose re-escalation is not permitted.

Patients must discontinue an investigational product if a criterion for investigational product withdrawal is met (see Section 10.1 and Appendix 2).

Once an investigational product has been discontinued, patients who had been receiving combination therapy may continue to receive the other investigational product as monotherapy, at the Investigator's discretion. This is applicable to both treatment arms of the study. Reintroduction of the discontinued investigational product at a later time during the active treatment phase is not permitted.

Detailed rules for dose adjustments of neratinib, lapatinib, and capecitabine in case of toxicity are provided in Appendix 2.

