
Grade 1 Diarrhea: Increase of <4 stools per day over baseline; mild increase in output compared to baseline. OR Grade 2 Diarrhea: Increase of 4-6 stools per day over baseline; moderate increase in ostomy output compared to baseline. Lasting ≤5 days OR Grade 3 Diarrhea: Increase of ≥7 stools per day over baseline; incontinence; hospitalization indicated; severe increase in ostomy output compared to baseline; limiting self-care and activities of daily living. Lasting ≤2 days
	
 • Adjust antidiarrheal treatment per the guidelines for management of diarrhea at the first onset of diarrhea (refer to Section 7.1.1). • Continue neratinib and capecitabine at full doses. • Instruct patient to follow dietetic recommendations in the guidelines for management of diarrhea (refer to Section 7.1.1). • Fluid intake of ~2 L/day should be maintained to avoid dehydration. • Once the event resolved to Grade ≤1 or baseline, start loperamide 4 mg with each subsequent neratinib administration.

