Abbreviations: BID: twice daily; L: liter; NCI CTCAE v.4.0: National Cancer Institute Common Terminology Criteria for Adverse Events Version 4.0.

Hand and Foot Syndrome

Guidelines for dose adjustments of **neratinib** and **capecitabine** for toxicity of Hand and Foot syndrome (Palmar-Plantar Erythrodysesthesia syndrome) due to combination of neratinib plus capecitabine are shown in Table A2. 7.

Table A2. 7 Hand-and-Foot Syndrome (Palmar-Plantar Erythrodysesthesia Syndrome) Requiring Dose Adjustment of Neratinib and Capecitabine

NCI CTCAE v.4.0	Action
Grade 1: Minimal skin changes or dermatitis (e.g., erythema, edema, or hyperkeratosis) without pain	
 Continue neratinib and capecitabine at starting dose.
Grade 2: Skin changes, e.g., peeling, blisters, edema, or hyperkeratosis, with pain; limiting instrumental ADL. PI: painful erythema and swelling of the hands and/or feet and/or discomfort affecting ADL.	
 Continue neratinib at starting dose level and hold capecitabine until recovery or to \leq grade 1, then resume at starting dose. If the event recurs/persists, continue neratinib at starting dose level and reduce capecitabine dose to 1100 mg/m² (550 mg/m² BID).
Grade 3: Severe skin changes, e.g., peeling, blisters, edema, or hyperkeratosis, with pain; limiting self-care ADL. PI: moist desquamation, ulceration, blistering or severe pain of the hands and/or feet and/or severe discomfort limiting self-care ADL.	
 Continue neratinib at starting dose level and hold capecitabine until recovery or to grade \leq 1, then reduce dose to 1100 mg/m² (550 mg/m² BID). If the event recurs/persists, continue neratinib at starting dose level and reduce capecitabine dose to 750 mg/m² (375 mg/m² BID).

Abbreviations: ADL, activities of daily living; BID, twice daily; NCI CTCAE v.4.0: National Cancer Institute Common Terminology Criteria for Adverse Events Version 4.0.

LAPATINIB PLUS CAPECITABINE

General Toxicities

Guidelines for dose adjustments of **lapatinib** and **capecitabine** for general toxicities due to combination of lapatinib plus capecitabine are shown in Table A2. 8.

Table A2. 8 General Toxicities Requiring Dose Adjustment of Lapatinib and Capecitabine

NCI CTCAE v.4.0	Action
Grade 2 adverse reaction	

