• 1st appearance	• Hold lapatinib and capecitabine until event resolves to Grade ≤ 1 ; then resume lapatinib dose at 1250 mg and capecitabine at the starting dose level.
• 2nd appearance	• Hold lapatinib and capecitabine until event resolves to Grade ≤ 1 ; then resume lapatinib dose at 1000 mg and capecitabine dose at 1500 mg/m ² (750 mg/m ² BID).
• 3rd appearance	• Discontinue lapatinib permanently. • Hold capecitabine until event resolves to Grade ≤ 1 ; then resume capecitabine at 1000 mg/m ² (500 mg/m ² BID).
• 4th appearance	• Discontinue capecitabine permanently.
Grade 3 adverse reaction	
• 1st appearance	• Hold lapatinib and capecitabine until event resolves to Grade ≤ 1 ; then resume lapatinib dose at 1250 mg and capecitabine dose at 1500 mg/m ² (750mg/m ² BID).
• 2nd appearance	• Hold lapatinib and capecitabine until event resolves to Grade ≤ 1 ; then resume lapatinib dose at 1000 mg and capecitabine at 1000 mg/m ² (500 mg/m ² BID).
• 3rd appearance	• Discontinue lapatinib and capecitabine permanently.
Grade 4 adverse reaction	
1st appearance	• Discontinue lapatinib and capecitabine permanently OR if Investigator deems it to be in the patient's best interest to continue, hold lapatinib and capecitabine until resolved to Grade ≤ 1 ; then resume lapatinib at 1000 mg and capecitabine at 1000 mg/m ² (500 mg/m ² BID).

Abbreviations: BID, twice daily; NCI CTCAE v.4.0: National Cancer Institute Common Terminology Criteria for Adverse Events Version 4.0.

Gastrointestinal Toxicity

Guidelines for dose adjustments of **lapatinib** and **capecitabine** for gastrointestinal toxicity are shown in Table A2. 9.

Table A2. 9 Gastrointestinal Toxicities Requiring Dose Adjustment of Lapatinib and Capecitabine

NCI CTCAE v.4.0	Action
Grade 1: Increase of <4 stools per day over baseline; mild increase in ostomy output compared to baseline.	
 Continue lapatinib and capecitabine at starting dose. Instruct patient to follow dietetic recommendations provided at the start of the study. Fluid intake of ~2L should be maintained to avoid dehydration.

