Grade 2: Increase of 4-6 stools per day over baseline; moderate increase in ostomy output compared to baseline.	
 Continue lapatinib and hold capecitabine until recovery to ≤ Grade 1 or baseline. Consider prophylactic antidiarrheal medications with next investigational product administration. If recovery occurs in ≤1 week of treatment being held, resume capecitabine at starting dose. If event persists/recurs, or if recovery occurs within 1-3 weeks of treatment being held, reduce dose of lapatinib to 1000 mg and capecitabine to 1500 mg/m² (750 mg/m² BID). Following reoccurrence of Grade 2, adjust next dose of capecitabine to 1000 mg/m² (500 mg/m² BID).

Grade 1 or 2 with complicating features (moderate to severe abdominal cramping, nausea or vomiting ≥ NCI CTCAE Grade 2, decreased performance status, fever, sepsis, neutropenia, frank bleeding, or dehydration)
 
or
 
Grade 3: Increase of ≥7 stools per day over baseline; incontinence; hospitalization indicated; severe increase in ostomy output compared to baseline, limiting self-care ADL.
	
 Hold lapatinib and capecitabine until recovery to ≤Grade 1 or baseline. May require administration of oral or IV fluids and electrolytes. Consider prophylactic antidiarrheal medications with next investigational product administration. If recovery occurs in ≤1 week of treatment being held, resume lapatinib and capecitabine at starting dose. If event persists/recurs, or if recovery occurs within 1-3 weeks of treatment being held, reduce lapatinib dose to 1000 mg and capecitabine dose to 1500 mg/m² (750 mg/m² BID).
Grade 4: Life-threatening consequences; urgent intervention indicated.	
 Discontinue lapatinib permanently. Hold capecitabine until recovery to ≤ Grade 1 or baseline. Consider prophylactic antidiarrheal medications with next investigational product administration. If recovery occurs in ≤1 week of treatment being held, resume capecitabine at starting dose. If event persists/recurs, or if recovery occurs within 1-3 weeks of treatment being held, reduce dose of capecitabine to 1500 mg/m² (750 mg/m² BID).

NCI CTCAE v.4.0	Action
	
 Following reoccurrence of Grade 4, discontinue capecitabine permanently.

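### Several Appendix 2 rows restart treatment at the starting dose or a fixed dose with no condition on earlier reductions, while Section 6.1.3 bars re-escalation, and no text says which governs

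*Protocol*

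**What the plan says.** Protocol Section 6.1.3 (Dose Adjustment) sets the general rule. After a reduction, "all subsequent cycles must be administered at that dose, unless further dose reduction is required. Dose re-escalation is not permitted". The same section makes the adjustment guidelines binding as a floor, lets investigators take further measures, and then refers sites onward: "Detailed rules for dose adjustments of neratinib, lapatinib, and capecitabine in case of toxicity are provided in Appendix 2".

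These Appendix 2 rows give a restart dose with no condition on an earlier reduction:

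- Table A2.1 (general toxicities, Arm A), Grade 2 first appearance: both drugs restart at the starting dose.
- Table A2.7 (hand-foot syndrome, Arm A), Grade 2: "Continue neratinib at starting dose level and hold capecitabine until recovery", after which capecitabine restarts at the starting dose.
- Table A2.8 (general toxicities, Arm B), Grade 2 first appearance: lapatinib restarts at 1250 mg and capecitabine at the starting dose. Grade 3 first appearance: "then resume lapatinib dose at 1250 mg and capecitabine dose at 1500" mg/m².
- Table A2.9 (gastrointestinal, Arm B), recovery in one week or less. For Grade 3 or complicated diarrhea: "resume lapatinib and capecitabine at starting dose". The Grade 2 and Grade 4 rows do the same for capecitabine alone.
- Table A2.14 (hand-foot syndrome, Arm B), Grade 2: capecitabine restarts at the starting dose.

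Other rows tell sites to continue at the starting dose (parts of A2.7, A2.9 and A2.14). The first row of Table A2.2 says "Continue neratinib and capecitabine at full doses".

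**The concern.** The starting dose is a defined amount in Tables 2 to 5, not a label for whatever the patient is taking. The rows above read as if the patient had never been reduced. For a patient who has been, a site following the table literally would raise the dose just after a new toxicity, and a site following Section 6.1.3 would not. This is a contradiction in a safety rule, and it occurs in both arms. If sites read it differently, the summaries of dose reductions and relative dose intensity (Protocol Section 12.2.3, SAP Section 7) would also be harder to interpret.

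**Working it through.** The plan gives no figure to reproduce here. The check sets the rows beside the dose levels.

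**Inputs** (Protocol Section 6.1.3, Tables 2 to 5):

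| Drug | Starting | Level -1 | Level -2 |
|---|---|---|---|
| Neratinib, mg | 240 | 160 | 120 |
| Capecitabine Arm A, mg/m² daily | 1500 | 1100 | 750 |
| Lapatinib, mg | 1250 | 1000 (750 in severe hepatic impairment) | none |
| Capecitabine Arm B, mg/m² daily | 2000 | 1500 | 1000 |

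**Formula:** implied change = dose stated in the row ÷ current dose − 1.

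**Sequences that the tables themselves allow:**

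| Earlier reduction | Later event and row | Arithmetic | Implied change |
|---|---|---|---|
| A2.8, second Grade 2: lapatinib to 1000 mg | A2.8, first Grade 3 | 1250/1000 − 1 | +25% |
| A2.6, Grade 3 hematologic: capecitabine to 1100 | A2.7, Grade 2 hand-foot | 1500/1100 − 1 | +36% |
| A2.13, Grade 3 hematologic: capecitabine to 1500 | A2.14, Grade 2 hand-foot | 2000/1500 − 1 | +33% |
| A2.2, diarrhea recovering in 1 to 3 weeks: neratinib to 160 mg | A2.1, first Grade 2 | 240/160 − 1 | +50% |
| A2.12, LVEF decline: lapatinib to 1000 mg | A2.9, Grade 3 diarrhea recovering in 1 week or less | 1250/1000 − 1 | +25% |

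The first sequence stays inside one table, and the worse event carries the higher lapatinib dose. It assumes that appearances are counted within grade, as Table A2.8 is laid out. Capecitabine does not change on that path (1500/1500 − 1 = 0).

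From level -2, a return to the starting dose is a doubling: 240/120, 1500/750 and 2000/1000 each give +100%.

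**Limit on fixed-dose rows.** A row that states an amount conflicts with Section 6.1.3 only if the current dose is below that amount. Table A2.1, Grade 3 first appearance (160 mg and 1100 mg/m²), therefore conflicts only for a patient already at level -2: 160/120 − 1 = +33% and 1100/750 − 1 = +47%.

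**Contrast within the appendix.** Table A2.6 keeps neratinib at whatever dose the patient is on. The second row of Table A2.2 asks whether neratinib has already been lowered before it says what to do. So the appendix allows for earlier reductions in some places, and the rows listed above do not.

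**The case against.** The best reply is that Section 6.1.3 already settles the matter. It is a flat prohibition, and the tables are introduced as guidelines. Because the guidelines are a floor and stricter measures are allowed, a site that does not escalate can say that it satisfies both texts. This has force, and it makes Section 6.1.3 the likelier reading. It does not remove the conflict, because Section 6.1.3 requires investigators to follow the guidelines and points to Appendix 2 as the detailed source. Its own lapatinib paragraph also allows a restart at 1250 mg after a first toxicity without mentioning an earlier reduction. A careful reader who has seen the wording of A2.6 could take the starting dose literally elsewhere.

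A second reply is that a patient on 160 mg cannot continue at 240 mg, so the continue rows describe patients still at full dose. That is a fair reading. Those rows, including the neratinib half of the A2.7 Grade 2 row, are ambiguous and weaker evidence than the restart rows.

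Third, Table A2.9 sends recurrent or persistent diarrhea to a reduction. Its conflict therefore mainly needs an earlier reduction for a different toxicity. This stands.

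A reader might also count the Grade 2 pneumonitis row of Table A2.3, "Reduce neratinib to 160 mg or discontinue neratinib", as raising a patient from 120 to 160 mg. The documents do not support that: an instruction to reduce cannot direct an increase, and the row offers discontinuation as the alternative.

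**Conclusion.** The inconsistency is real and confined to the rows listed. It matters only for a patient whose current dose is below the dose that the row states. Read literally, one step back up is +25% for lapatinib, +33% or +36% for capecitabine and +50% for neratinib. These are sizes of the implied step, not predictions of what sites would do.

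Three stronger conclusions are tempting and unsupported:

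- A reader might say that the protocol orders dose increases. It does not, because Section 6.1.3 forbids them. The defect is that two binding texts disagree and neither is named as prevailing.
- A reader might multiply the background rates, 29% dose reduction for diarrhea and 47% hand-foot syndrome, to get a number of affected patients. The first rate comes from neratinib monotherapy and the second is any-grade in a different study of the combination. This trial mandates antidiarrheal prophylaxis in Arm A, independence is unknown, and order and grade decide whether the conflict arises. The product would be neither an estimate nor a bound.
- A reader might assume that two separate toxicities are typical in this trial. No passage says so.

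Differing practice between sites is possible but not shown. Sample size, power and alpha are unaffected. The correction should be made because the rule bears on safety and the remedy is cheap.

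**What to change.** Reconcile Section 6.1.3 with the restart rows in Tables A2.1, A2.7, A2.8, A2.9 and A2.14, and clear up the ambiguous continue rows in A2.2, A2.7, A2.9 and A2.14 at the same time. Add one sentence, in Section 6.1.3 or at the head of Appendix 2, stating which text governs for a patient whose dose has already been reduced. The sponsor's clinical team decides the rule; this review takes no position on the dose. The cost is wording carried in a protocol amendment, with no added procedures, visits or patients.
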